### 9.3 Confirmatory Measurement/Duration of Response

Biopsy will be performed for confirmatory measurement.

### 9.4 Progression-Free Survival

N/A

### 9.5 Response Review

Final response review will be conducted four weeks after the last of 3 treatment sessions for the treatment arm or the last of 3 study visits for controls.

## 10.0 ADVERSE EVENT REPORTING

The descriptions and grading scales found in the revised NCI Common Terminology Criteria for Adverse Events (CTCAE) version 4.0 will be utilized for adverse event reporting. A copy of the CTCAE version 4.0 can be downloaded from the CTEP web site (<http://ctep.cancer.gov>).

### 10.1 Definitions

10.1.1 **Adverse events**(AE's) will use the descriptions and grading scales found in the NCI Common Terminology Criteria for Adverse Events (CTCAE v 4.0) in Appendix II.

**Adverse events:** Any unfavorable and unintended sign (including abnormal laboratory finding), symptom, or disease temporally associated with the use of a medical treatment or procedure, regardless of whether it is considered related to the medical treatment or procedure (attribution of unrelated, unlikely, possible, probable, or definite). Each AE is a unique representation of a specific event used for medical documentation and scientific analysis.

10.1.2 A **serious adverse event (SAE)** is defined by the federal regulations as any adverse event that:

- Results in death; or is
- Life threatening; or
- Results in permanent impairment of body function or permanent damage to a body structure; or
- An event requires medical or surgical intervention to prevent permanent impairment or damage to a body function or body structure.

SAE's are defined by FDA and therefore seriousness (not severity) serves as a guide for defining regulatory reporting obligations for patient/subject safety. **Serious** is based on patient/event outcome or action criteria usually associated with events that pose a threat to a patient's life or functioning.

The definition of serious adverse event (experience) also includes **important medical events**. Medical and scientific judgment should be exercised in deciding whether reporting is appropriate in other situations, such as important medical events that may not be immediately life-threatening or result in death or hospitalization but may jeopardize the patient or **may require intervention** to prevent one of the other outcomes listed in the definition above. These should also usually be considered serious. Examples of such events are intensive treatment in an emergency room or at home for allergic bronchospasm; blood dyscrasias or convulsions that do not result in hospitalization; or development of drug dependency or drug abuse.

10.1.3 **Expected events** are those that have been previously identified as resulting from administration of the agent. For this study, these include:

Likely:

- Pain of the skin
- Edema
- Erythema and/or purpura
- Temporary skin hypopigmentation or hyperpigmentation

Unlikely:

- Hematoma

- Scarring
- Herpes Simplex Virus outbreak if treating an area with past recurrent outbreaks, usually around the mouth
- Skin infection
- Skin ulceration/ bullous dermatitis

Any of these key adverse events that are greater than grade III according to CTCAE, are not expected.

10.1.4 An adverse event is considered **unexpected** when either the type of event or the severity of the event is *not* listed in: the device brochure, or the device information section of this protocol.

10.1.5 The definition of **related** is that there is a reasonable possibility that the device caused the adverse experience.

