### 10.2.1 Determination of Reporting Requirements

Reporting requirements may include the following considerations:

- 1) whether the patient has received an investigational or commercial agent;
- 2) the characteristics of the adverse event including the grade (severity), the relationship to the study therapy (attribution), and the prior experience (expectedness) of the adverse event;

- 3) the Phase (1, 2, or 3) of the trial; and 4) whether or not hospitalization or prolongation of hospitalization was associated with the event.

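### The serious adverse event criteria in 10.1.2 omit hospitalization, although the same section is worded as if it were listed, so seriousness of an admitted event can rest on judgement alone

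*Combined protocol and SAP*

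**What the plan says.** Section 10.1.2 gives four criteria for a serious adverse event:

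1. "Results in death; or is"
2. "Life threatening; or"
3. "Results in permanent impairment of body function or permanent damage to a body structure"
4. "An event requires medical or surgical intervention to prevent permanent impairment or damage to a body function or body structure"

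A later paragraph of 10.1.2 extends the definition, by medical and scientific judgement, to important medical events that "may not be immediately life-threatening or result in death or hospitalization but may jeopardize the patient". It also covers events that may need intervention to avert one of the outcomes listed earlier. Its examples include intensive emergency-room or home treatment, and blood disorders or convulsions without admission.

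Section 10.2.1 says that reporting requirements may take several considerations into account. The fourth is "whether or not hospitalization or prolongation of hospitalization was associated with the event".

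Sections 5.2, 10.3.2.1, 10.3.3.1 and 10.3.4 each set a duty that applies when an event is serious, some with further conditions.

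**The concern.** The important-medical-events paragraph is a supplement. It picks up events that fall short of the listed outcomes but still deserve to be treated as serious. Describing those events as ones that may not lead to death or hospitalization makes sense only if both are already on the list. Death is; hospitalization is not. The definition therefore relies on a criterion that it does not contain.

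Admission to hospital is a fact that can be read from the record. Under the current text it does not by itself make an event serious. Two investigators could classify the same admitted event differently and both be within the protocol.

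Safety is the secondary objective (2.2), and the protocol describes this as the first use of the combined laser for this indication, with a commitment to watch closely for new or concerning reactions. The trial is also small, so there is little chance that a pattern across many subjects would make up for one event that was classified too low.

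**Working it through.** No arithmetic applies. The check sets the definition beside the wording that depends on it, then traces one kind of event through each reporting rule.

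**Step 1: is hospitalization in the list?** None of the four criteria (0 of 4) mentions it. The items are joined by *or* and the last closes with a full stop, so the list reads as complete and nothing suggests a line lost in extraction.

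**Step 2: where does section 10 mention hospitalization?** In three places: twice in the important-medical-events paragraph of 10.1.2 and once in 10.2.1. The first two describe events without admission. The third is a permissive consideration. None makes admission a criterion for seriousness or a trigger for a report.

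**Step 3: the test event.** Take an event that leads to admission but is not fatal, not life-threatening and not permanently impairing, and that needs no intervention to prevent impairment. It meets none of the four criteria. It becomes serious only through the judgement clause. Suppose the investigator does not so judge it.

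| Route | Conditions in the protocol | Result for the test event |
|---|---|---|
| 5.2, IRB report of events found at visits | serious | missed |
| 10.3.2.1, manufacturer, three work days | serious and unexpected | missed, even if unexpected |
| 10.3.3.1, main IRB rule, ten working days | serious, unexpected, related or possibly related, and suggesting greater risk than known | missed, even if the other three hold |
| 10.3.4, follow-up until resolution, an acceptable endpoint or loss to follow-up | serious | missed |
| 10.3.3.1, second IRB rule, ten working days | more frequent or more severe than expected; seriousness not required | still caught if the condition holds |
| 10.3 and 10.3.3, institutional policy | all adverse events | depends on a policy not in the documents |
| 13.3.3, safety table | possibly, probably or definitely related; seriousness not required | still counted if related |

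Section 10.3 also requires device-related serious injuries to be reported to the manufacturer within three work days. The protocol does not define that term or tie it to 10.1.2, so the outcome on that route cannot be settled from the text.

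**Step 4: what the missing bullet changes.** For 5.2 and 10.3.4, seriousness is the only condition on the event, so classification alone decides whether the duty applies. For 10.3.2.1 and the main rule in 10.3.3.1, classification decides only when the other conditions are also met.

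**The case against.** The strongest reply is that an admitted event is not shut out. The important-medical-events paragraph is illustrative and does not exclude admitted events. If intensive emergency-room treatment without admission should usually count as serious, a sensible investigator would hardly rate a comparable admitted event lower. The fourth criterion may also cover many admissions, since inpatient treatment is often given to prevent lasting damage. This stands in part: many admitted events would probably be classified as serious. It does not remove the inconsistency, and it leaves an objective outcome to discretion.

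A second reply is that other safeguards exist: the second IRB rule in 10.3.3.1, institutional policy, withdrawal with immediate supportive care for related grade III toxicity (11.2), and the monitoring committee's review of adverse event data (Appendix III). These also stand, and they limit the consequence. None of them replaces the manufacturer report in 10.3.2.1 or the follow-up duty in 10.3.4.

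Three stronger readings are tempting, and the documents do not support them.

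- *An admitted skin infection would escape expedited reporting because of this gap.* Skin infection is a listed expected event (10.1.3). Unless its severity made it unexpected, 10.3.2.1 and the main IRB rule would not apply even with the bullet added. It may also meet the fourth criterion.
- *Section 10.2.1 contradicts the definition.* Its wording is permissive and lists general factors. It shows that hospitalization was thought relevant to reporting; the inconsistency itself lies within 10.1.2.
- *Events would be lost from the safety results, and the loss can be stated as a share of the laser arm.* Section 13.3.3 tabulates related events whatever their seriousness. Such a share would be one assumed event divided by the arm size, with no admission rate in the documents behind it.

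**Conclusion.** The point holds as an internal inconsistency in a safety definition that should be corrected. Hospitalization is missing from the four criteria, and the paragraph that supplements them is written as if it were there. An admitted event that meets none of the four is serious only by judgement. If it is not so judged, it falls outside four duties: IRB reporting under 5.2, the manufacturer report in 10.3.2.1, the main IRB rule in 10.3.3.1 and follow-up under 10.3.4. The two middle ones also have conditions beyond seriousness.

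The effect is limited to classification, expedited reporting and follow-up. The adverse event counts, the response analysis, the sample size and the table of p-values are untouched. The consequence is possible rather than certain, and its frequency cannot be estimated from the documents.

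The conclusion assumes that the four-item list is complete as printed. It does not rest on the federal definition to which 10.1.2 attributes its list, since that source was not checked. If the institutional policy already treats admission as serious, the practical gap for the IRB is smaller, but the protocol text would still need to be made consistent.

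**What to change.** Add a bullet to the list in 10.1.2 for initial or prolonged hospitalization. The definition then agrees with its own important-medical-events paragraph, and the consideration in 10.2.1 gains a counterpart in the rules of 10.3, because those rules already act on seriousness. No other reporting rule needs rewording for this purpose.

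The cost is one line of text and possibly an occasional extra expedited report. No change is needed to the visit schedule or the statistical analysis.

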## 10.2 Purpose

Adverse event data collection and reporting, which are required as part of every clinical trial, are done to ensure the safety of patients enrolled in the studies as well as those who will enroll in future studies using similar agents. Adverse events are reported in a routine manner at scheduled times during a trial (please follow directions for routine reporting provided in the Data Reporting Section). Additionally, certain adverse events must be reported in an expedited manner for more timely monitoring of patient safety and care. The following sections provide information about expedited reporting.

Events resulting from concurrent illnesses and reactions to concurrent medications must be reported as adverse events.

Any worsening of the patient's clinical condition while the patient is on study will be considered to be an adverse event unless it is within the normal range of disease fluctuation for that patient.

### 10.2.1 Determination of Reporting Requirements

Reporting requirements may include the following considerations:

- 1) whether the patient has received an investigational or commercial agent;
- 2) the characteristics of the adverse event including the grade (severity), the relationship to the study therapy (attribution), and the prior experience (expectedness) of the adverse event;

- 3) the Phase (1, 2, or 3) of the trial; and 4) whether or not hospitalization or prolongation of hospitalization was associated with the event.

#### 10.2.2 Steps to determine if an adverse event is to be reported in an expedited manner:

Step 1: *Identify the type of event using the NCI Common Terminology Criteria for Adverse Events (CTCAE) version 4.0.*

The CTCAE provides descriptive terminology and a grading scale for each adverse event listed. A copy of the CTCAE can be downloaded from the CTEP home page (<http://ctep.cancer.gov>). Additionally, if assistance is needed, the NCI has an Index to the CTCAE that provides help for classifying and locating terms. All appropriate treatment locations should have access to a copy of the CTCAE.

Step 2: *Grade the event using the NCI CTCAE.*

Step 3: *Determine whether the adverse event is related to the protocol therapy (investigational or commercial).*

Attribution categories are as follows: Unrelated, Unlikely, Possible, Probable, and Definite.

Step 4: *Determine the prior experience of the adverse event.*

Step 5: *Review Table 10.1 to determine if there are any protocol-specific requirements for reporting of specific adverse events that require special monitoring.*

Step 6: *Determine if the protocol treatment given prior to the adverse event included investigational agent(s), a commercial agent(s), or a combination of investigational and commercial agents.*

NOTE: If the subject received at least one treatment with the investigational device serious adverse events will be reported as indicated in section 10.3.

### 10.3 Reporting Methods

All AEs and SAEs will be reported as per University of Miami's Human Subject Research Office Policy and Procedures. Any suspected medical device-related death will be reported to the manufacturer no later than three work days from the day that the PI or designee became aware of the event. All medical device-related serious injuries will be reported to

the manufacturer no later than three work days from the day that the PI or designee became aware of the event. At the discretion of the Sponsor, a malfunction may be reported to the FDA by using the voluntary Med Watch program to advise FDA of problems with medical devices.

### 10.3.2 FDA Reporting

#### 10.3.2.1 Investigational Agent reporting

All serious, unexpected adverse events must be reported to the manufacturer within three work days.

Fatal or life-threatening adverse events must be reported to the manufacturer within three work days from being made known to the Principal Investigator or designee.

### 10.3.3 IRB Reporting

All adverse events will be reported as per University of Miami's Human Subject Research Office Policy and Procedures.

10.3.3.1 All adverse events that are serious adverse events **and** are unexpected **and** are related or possibly related IRB **and** suggest that the research places subjects or others at greater risk of harm or discomfort than known or anticipated must be reported within ten (10) working days of being made known to the Principal Investigator. Events that are more frequent than anticipated or more severe than expected must be reported to the IRB within ten (10) working days of being made known to the Principal Investigator.

All unanticipated life-threatening events or deaths must be reported to the IRB within 24 hours of being made known to the Principal Investigator if the event is a direct outcome or possibly an outcome of the study intervention.

### 10.3.4 Follow-up Reporting

For all SAE's, the investigator is obligated to pursue and provide follow-up reporting information until the event has resolved or until an acceptable medical endpoint has been reached or the patient is lost to follow-up.

## **11.0 CRITERIA FOR DISCONTINUATION OF THERAPY**

Should any of the following occur, the subject will be immediately withdrawn from the study and receive timely supportive or standard care if necessary.

### **11.1 Disease progression**

Superficial and nodular basal cell carcinoma subtypes are considered less aggressive than other subtypes of BCC such as morpheaform or infiltrative. In addition, the rate of invasion is lower with smaller lesions. However, should there be obvious disease progression (10% increase in size) in either group throughout the short duration of the study, they will be immediately withdrawn and receive standard of care.

### **11.2 Unacceptable Adverse Events**

Likely side effects to treatment with this laser may include pain of the skin, erythema, purpura, or temporary hypo or hyperpigmentation of the skin. Unlikely reported side effects include hematoma, scarring, mild skin ulceration or bullous dermatitis, and skin infection. See section 7.1.12.

Any grade III non-lab toxicities that are possible, probably or definitely related to involvement in the study are unacceptable and subjects will receive immediate supportive care and be withdrawn from the study.

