## 5.4 Early discontinuation of therapy

Grading for adverse events as determined by US Department of Health Common Terminology Criteria for Adverse Events (CTCAE version 4.0)

Any subject with a non-laboratory Grade III or higher toxicity that is possibly, probably or definitely related to involvement in our study will be considered for removal.

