## **6.0 DOSING DELAYS/DOSE MODIFICATIONS**

### **6.1 Study Agent**

There are no expected dosing delays or dosing modifications for this study. Due to the fact we are testing specific laser parameters for the potential efficacy of clearing certain types of basal cell carcinomas, we will not be adjusting the settings.

However, should the subject experience any adverse effects secondary to the use of the multiplex laser, they will immediately be provided with supportive care tailored to the nature of the adverse effect (see section 4.2). In addition, there are no expected systemic toxicities. If the expected and unexpected effects are not tolerable, the subject may also withdraw from the study at any point.

In our study, early termination will be based on presence of intolerable side effects and desire to withdraw from studies. Should our treatment prove ineffective, all patients will receive standard treatment of care immediately.

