### **11.3 Patient wishes**

Should the subject wish to withdraw from the study, he/she may do so at any time. The subject may then continue to receive standard of care.

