### **11.4 Investigator discretion**

Should the subject no longer meet eligibility criteria, or should [name] deem the treatment inappropriate for the subject, he may elect to withdraw the subject at any time.

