### 13.2 Sample Size Justification/Accrual Rate

The analysis set (evaluable subjects) consist of study-eligible subjects who either complete three treatments/three study visits and the biopsy visitor are withdrawn from the study due to showing evidence of PD during the study (non-responder). Subjects will be non-evaluable when they do not wish to continue in the study, are unable to continue in the study, or they cannot complete treatments or study visits for any reason other than PD. There will be 15 evaluable subjects in the treatment arm and 5 evaluable subjects in the control (non-treatment) arm. We expect that three to four subjects in both treatment arm and control arm will be non-evaluable. Therefore, the planned maximum number of enrolled subjects will be 28. The number of subjects is small due to the preliminary nature of the study, yet similar in size to previous studies (Konnikov et al 2011 and Shah et al 2009), which only used the 595 nm laser. Out of our 15 subjects in the treatment arm, we expect eleven or more subjects will respond to proposed treatment (either CR or PR). The table below shows significance (p-value) of hypothetical study findings assuming one BCC per subject. As shown in the second row, if one out of five subjects in the control arm shows either CR or PR and twelve or more out of fifteen subjects in the treatment arm show either CR or PR then test of comparing proportions of two arms is statistically significant (p-value < 0.05). If none in the control arm show either CR or PR and nine or more out of fifteen subjects in the treatment arm have either CR or PR, we also get a statistically significant difference indicating a better response rate in the treatment arm.

Number of subjects (CR or PR) among 15 subjects in the treatment arm vs. 5 in control arm	p-value*
11 (73.3%) vs. 1 (20%)	0.058
12 (80%) vs. 1 (20%)	0.031
9 (60%) vs 0 (0%)	0.030

\* one-sided Fisher's exact test (assuming every subject has one BCC)

One to two subjects will be accrued per week secondary to availability of the laser.

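### Sections 5.4 and 11.2 conflict on withdrawal for related grade III toxicity, and the rule followed also decides whether the subject enters the response analysis

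*Combined protocol and SAP*

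**What the plan says.** **Withdrawal.** Section 5.4 covers non-laboratory toxicity of grade III or higher: subjects whose event is "possibly, probably or definitely related to involvement in our study will be considered for removal". Section 11.2 covers grade III non-laboratory toxicity with the same degrees of relatedness and says such events "are unacceptable and subjects will receive immediate supportive care and be withdrawn from the study". The lead-in to Section 11.0 is equally firm: "the subject will be immediately withdrawn from the study and receive timely supportive or standard care if necessary". Section 6.1 names no grade and says "early termination will be based on presence of intolerable side effects and desire to withdraw from studies". Sections 11.3 and 11.4 add two more routes out, the subject's own wish ("Should the subject wish to withdraw from the study, he/she may do so at any time") and the investigator's judgement ("deem the treatment inappropriate for the subject, he may elect to withdraw the subject at any time").

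**Analysis set.** Section 13.2 counts as evaluable those who complete three treatments or visits plus the biopsy visit, and those withdrawn for progression, who are non-responders (Section 4.0 agrees). Subjects are non-evaluable if, among other reasons, "they cannot complete treatments or study visits for any reason other than PD". The target is 15 evaluable laser subjects and 5 evaluable controls. On enrolment: "Therefore, the planned maximum number of enrolled subjects will be 28". Section 13.3.2 gives no all-treated or all-randomised response analysis.

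**The concern.** A site cannot treat one event as grounds for compulsory withdrawal and as a matter for consideration. The safety side is plain: Section 6.1 rules out changing the laser settings, so a subject kept on treatment after a related grade III event would go on at the same dose, and Section 2.2 describes this as the first use of the combination laser in these lesions.

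There is also an effect on the estimate. The trial is unblinded and lesions are measured at every visit (Section 5.2), so whoever chooses between 5.4 and 11.2 knows the arm and may know how the lesion is doing. That choice can decide whether the subject stays in the response rate or drops out and is replaced within the 28. Controls receive no laser (Section 4.1), so exclusion for laser toxicity falls on one arm only. The response rate is the primary endpoint and informs whether a larger trial is worthwhile (Sections 2.0 and 13.1).

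**Working it through.** **1. The rules side by side**, for a related non-laboratory event.

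| Section | Grade | Action |
|---|---|---|
| 5.4 | III or higher | Removal considered |
| 11.0 and 11.2 | III (nothing said about higher) | Withdrawn at once |
| 6.1 | None named | General statement on tolerability and subject choice; no reference to Section 11 |

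The direct conflict is between the first two rows.

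**2. Consequence under 13.2**, for an event before the day-84 biopsy.
- Withdrawn under 11.2: not progression, so non-evaluable, and the place can be refilled.
- Retained under 5.4 and completes: evaluable and analysed.

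**3. The plan's own figures.** Inputs from Section 13.2: 15 laser and 5 control subjects, one BCC each, one-sided Fisher's exact test. With n laser subjects, r responders in total and b₀ control responders,

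p = Σ(b=0 to b₀) C(n, r−b)·C(5, b) / C(n+5, r).

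- 12/15 vs 1/5: (105 + 2,275)/77,520 = 0.0307 (plan 0.031).
- 11/15 vs 1/5: 0.0578 (plan 0.058).
- 9/15 vs 0/5: 0.0298 (plan 0.030).

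All three reproduce. Enrolment reproduces as 15 + 5 + 4 + 4 = 28, reading the expected loss of three to four as per arm. The 8 spare places cover every non-progression reason in both arms, so they are not a toxicity estimate.

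**4. One subject, 5.4 against 11.2.** Assumption: one laser subject has a qualifying event and would complete if retained. Start from the plan's expected minimum for the laser arm, 11/15, with 1/5 in controls (73%, p=0.058).
- A non-responder is withdrawn and not replaced: 11/14 (79%), p=0.038.
- A non-responder is withdrawn and replaced by a responder: 12/15 (80%), p=0.031.
- A non-responder is withdrawn and replaced by a non-responder: 11/15, p=0.058, unchanged.
- A responder is withdrawn and not replaced: 10/14 (71%), p=0.071.

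**5. Replaced withdrawals put back in the denominator.** Assumption: one or two laser subjects were excluded for toxicity and replaced.

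| Reported result | Put back | All non-responders | All responders |
|---|---|---|---|
| 12/15 vs 1/5 (80%, p=0.031) | 1 | 12/16 (75%), p=0.048 | 13/16 (81%), p=0.025 |
| 12/15 vs 1/5 (80%, p=0.031) | 2 | 12/17 (71%), p=0.067 | 14/17 (82%), p=0.021 |
| 9/15 vs 0/5 (60%, p=0.030) | 1 | 9/16 (56%), p=0.039 | 10/16 (63%), p=0.023 |

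For example, 12/16 vs 1/5 is (560 + 9,100)/203,490 = 0.0475, 13/16 vs 1/5 is (120 + 2,800)/116,280 = 0.0251, and 14/17 vs 1/5 is (136 + 3,400)/170,544 = 0.0207. Putting back none leaves the reported result unchanged.

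**The case against.** **Section 11 evidently leads.** It is the section on discontinuation, its lead-in is mandatory, and Appendix III gives the monitoring committee Sections 7.1.12 and 11.0, not 5.4, as its safety guidance. This shows which way to resolve the conflict. It does not remove the wording of 5.4, which a site may follow in good faith.

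**Section 6.1.** A reader might infer a third, competing grade III rule. The text does not support that: it names no grade and largely restates what 11.3 allows. It needs only a cross-reference.

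**The evaluable set is a legitimate choice.** It is prespecified, response uses the day-84 histology (Section 9.2), and a subject withdrawn earlier has no such result. Progression is itself a response category, so counting it as non-response while excluding toxicity withdrawals is not an inconsistency. This stands. A reader might infer that the primary analysis must impute non-response; in a pilot that is a debatable estimand choice, and the documents do not require it.

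**Direction and size.** A reader might also infer that the exclusion flatters the laser. Nothing in the documents says that subjects with toxicity respond less often, and the table in the working runs both ways. No grade III rate is given, the likely effects listed in Section 7.1.12 carry no grade, and no stated decision depends on p<0.05, so movement across 0.05 carries little weight.

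**Reporting.** Section 13.3.3 tabulates related events and 13.5 says excluded data will be reported. These subjects are therefore not lost to safety reporting, but neither section restores them to a response rate or asks for counts by arm and reason.

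**Conclusion.** The conflict between 5.4 and 11.0/11.2 is real and should be removed. It is first a safety contradiction. It also leaves open, in an unblinded trial, whether a subject with a related grade III event is analysed. The exclusion in 13.2 is acceptable for a primary evaluable-set analysis, but for laser toxicity it can act only on the laser arm, and the plan has no analysis showing its effect.

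The size cannot be stated, because the documents give no grade III rate. If there is no such subject, nothing changes. With one excluded and replaced subject, a reported 80% response rate would be 75% or 81% depending on that subject's unobserved outcome, with one-sided p from 0.048 to 0.025. This assumes one BCC per subject and the plan's hypothetical 12/15 vs 1/5. The documents support neither a claim of upward bias nor a claim that the primary analysis is invalid.

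**What to change.** **Wording.**
- Section 5.4: replace the discretionary phrase with *will be withdrawn (see 11.2)*.
- Section 11.2: write *grade III or higher*.
- Section 6.1: replace the early-termination sentence with a reference to Section 11.0.

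**Analysis.** Keep the primary analysis as defined in 13.2. In 13.3.2 add: *As a sensitivity analysis, subjects withdrawn before the day-84 assessment because of toxicity at least possibly related to study involvement, whether under 11.2, 11.3 or 11.4, are counted as non-responders. Withdrawals are reported by arm and reason.* Tying this to study involvement matches the trigger in 11.2. If the lesion-level analysis is used, count all of such a subject's eligible BCCs as non-responding.

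**Cost.** Edits to four sections, one extra analysis and one small table. No extra subjects or visits. The supporting figure may look less favourable than the primary one, and for these subjects it mixes tolerability with tumour response. The judgement of relatedness and the discretion in 11.4 remain, so the reported reasons for withdrawal should be read alongside it.
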